APPENDIX C. QUALITY CONTROL AND QUALITY ASSURANCE

Protocol Amendments and Protocol Deviations and Violations

Protocol Amendments

No changes from the final approved (signed) protocol will be initiated without the prior written approval or favorable opinion of a written amendment by the independent ethics committee/institutional review board (IEC/IRB) and national and local competent authorities, as applicable, except when necessary to address immediate safety concerns to the patients or when the change involves only nonsubstantial logistics or administration. The Principal Investigator at each investigational center, the coordinating investigator (if applicable), and the sponsor will sign the protocol amendment.

Protocol Violations

Any deviation from the protocol that affects, to a significant degree, (a) the safety, physical, or mental integrity of the patients in the study and/or (b) the scientific value of the study will be considered a protocol violation. Protocol violations may include non-adherence on the part of the patient, the investigator, or the sponsor to protocol-specific inclusion and exclusion criteria, primary objective variable criteria, or Good Clinical Practice (GCP) guidelines; noncompliance to investigational medicinal product (IMP) administration; use of prohibited medications.

Protocol violations will be identified and recorded by investigational center personnel in the case report form (CRF). All protocol violations will be reported to the responsible IEC/IRB, as required.

When a protocol violation is reported, the sponsor will determine whether to discontinue the patient from the study or permit the patient to continue in the study, with documented approval from the medical expert. The decision will be based on ensuring the safety of the patient and preserving the integrity of the study.

Changes in the inclusion and exclusion criteria of the protocol are **not** prospectively granted by the sponsor. If investigational center personnel learn that a patient who did not meet protocol inclusion and exclusion criteria was entered in a study, they must immediately inform the sponsor of the protocol violation. If such patient has already completed the study or has withdrawn early, no action will be taken but the violation will be recorded.

Information to Study Personnel

The investigator is responsible for giving information about the study to all personnel members involved in the study or in any element of patient management, both before starting the study and during the course of the study (eg, when new personnel become involved). The investigator must ensure that all study personnel are qualified by education, experience, and training to perform their specific task. These study personnel members must be listed on the investigational center authorization form, which includes a clear description of each personnel member's responsibilities. This list must be updated throughout the study, as necessary.

The study monitor is responsible for explaining the protocol to all study personnel, including the investigator, and for ensuring they comply with the protocol.

Study Monitoring

To ensure compliance with GCP guidelines, the study monitor or representative is responsible for ensuring that patients have signed the informed consent form and the study is conducted according to applicable Standard Operating Procedures (SOPs), the protocol, and other written instructions and regulatory guidelines.

The study monitor is the primary association between the sponsor and the investigator. The main responsibilities of the study monitors are to visit the investigator before, during, and after the study to ensure adherence to the protocol, that all data are correctly and completely recorded and reported, and that informed consent is obtained and recorded for all patients before they participate in the study and when changes to the consent form are warranted, in accordance with IEC/IRB approvals.

The study monitors will contact the investigator and visit the investigational center according to the monitoring plan. The study monitor will be permitted to review and verify the various records (CRFs and other pertinent source data records, including specific electronic source document relating to the study) to verify adherence to the protocol and to ensure the completeness, consistency, and accuracy of the data being recorded.

As part of the supervision of study progress, other sponsor personnel may, on request, accompany the study monitor on visits to the investigational center. The investigator and assisting personnel must agree to cooperate with the study monitor to resolve any problems, errors, or possible misunderstandings concerning the findings detected during the course of these monitoring visits or provided in follow-up written communication.

Audit and Inspection

The sponsor may audit the investigational center to evaluate study conduct and compliance with protocols, SOPs, GCP guidelines, and applicable regulatory requirements. The sponsor's Global Clinical Quality Assurance, independent of Global Specialty Development, is responsible for determining the need for (and timing of) an investigational center audit.

The investigator must accept that competent authorities and sponsor representatives may conduct inspections and audits to verify compliance with GCP guidelines.

APPENDIX D. ETHICS

Informed Consent/Assent

The investigator, or a qualified person designated by the investigator, should fully inform the patient of all pertinent aspects of the study, including the written information approved by the IEC/IRB. All written and oral information about the study will be provided in a language as nontechnical as practical to be understood by the patient. The patient should be given ample time and opportunity to inquire about details of the study and to decide whether or not to participate in the study. The above should be detailed in the source documents.

Written informed consent will be obtained from each patient before any study specific procedures or assessments are done and after the aims, methods, anticipated benefits, and potential hazards are explained. The patient's willingness to participate in the study will be documented in the informed consent form, which will be signed and personally dated by the patient and by the person who conducted the informed consent discussion. The investigator will keep the original informed consent forms, and copies will be given to the patients. It will also be explained to the patients that the patient is free to refuse participation in the study and free to withdraw from the study at any time without prejudice to future treatment.

The investigator, or a qualified person designated by the investigator, should fully inform the patient and *<each>* parent/legally acceptable representative of all pertinent aspects of the study, including the written information approved by the IEC/IRB. All written and oral information about the study will be provided in a language as nontechnical as practical to be understood by the *<each>* parent/legally acceptable representative and the patient. The patient and *<each>* parent/legally acceptable representative should be given ample time and opportunity to inquire about details of the study and to decide whether or not to participate in the study. The above should be detailed in the source documents.

A personally signed and dated informed consent form will be obtained from *<each>* parent/legally acceptable representative, and a signed and dated assent form will be obtained from each patient (if the patient is able) before any study specific procedures or assessments are done and after the aims, methods, anticipated benefits, and potential hazards are explained; according to IEC/IRB requirements. The forms will be signed and dated also by the person who conducted the informed consent discussion. The investigator will keep the original informed consent and assent forms, and copies will be given to the patients (and *<each>* parent/legally acceptable representative). It will also be explained to the patients (and *<each>* parent/legally acceptable representative) that they are free to refuse participation in the study and free to withdraw from the study at any time without prejudice to future treatment.

Competent Authorities and Independent Ethics Committees/Institutional Review Boards

Before this study starts, the protocol will be submitted to the national competent authority and to the respective IEC/IRB for review. As required, the study will not start at a given investigational center before the IEC/IRB and competent authority (as applicable) for the investigational center give written approval or a favorable opinion.

Confidentiality Regarding Study Patients

The investigator must ensure that the privacy of the patients, including their identity and all personal medical information, will be maintained at all times. In CRFs and other documents or image material submitted to the sponsor, patients will be identified not by their names, but by an identification number.

Personal medical information may be reviewed for the purpose of patient safety or for verifying data in the source and the CRF. This review may be conducted by the study monitor, properly authorized persons on behalf of the sponsor, Global Quality Assurance, or competent authorities. Personal medical information will always be treated as confidential.

Registration of the Clinical Study

In compliance with national and local regulations and in accordance with Teva standard procedures, this clinical study will be registered on trials registry websites.

APPENDIX E. WOMEN OF CHILDBEARING POTENTIAL AND BIRTH CONTROL METHODS

The following is standard in current Teva protocols:

Contraception recommendations and pregnancy testing should encompass all investigational medicinal products (IMP)s as well as non-IMPs, eg, background therapy, and the measures to be followed should be based on the medicinal product with highest risk.

Assessment of likelihood of possible interaction between IMP or concomitant medications and hormonal contraception should be conducted. Hormonal contraception may be susceptible to interaction with the IMP, which may reduce the efficacy of the contraception method, eg, CYP 4A inducers. In case of suspected interaction, hormonal contraceptive alone may not be sufficient. In the absence of clinical pharmacokinetic (PK) interaction study data in IMPs with demonstrated or suspected human teratogenicity/fetotoxicity, recommendation for use of hormonal contraceptives should be thoroughly justified by the sponsor. Additional contraceptive methods, including supplementary barrier methods, may be considered.

Women/Girls of childbearing potential are defined as:

- not surgically (documented hysterectomy, bilateral oophorectomy, or bilateral salpingectomy) or congenitally sterile
- not postmenopausal

Postmenopausal women:

- 1 year postmenopausal (no menses for 12 months without an alternative medical cause plus an increased concentration of follicle stimulating hormone of more than 35 U/L) in women not using hormonal contraception or hormonal replacement therapy

Recommendations for application of birth control methods:

- IMPs with Marketing Authorisation (MA)
 - Summary of Product Characteristics (SmPC): in case of no contraception recommendations, the principles of IMPs without MA should be applied
- IMPs without MA
 - All female reproduction toxicity studies and standard battery of genotoxicity tests should be completed before the inclusion, in any clinical trial, of women of childbearing potential (WOCBP) not using highly effective birth control or whose pregnancy status is unknown (in compliance with International Council for Harmonisation module 2 [ICH M2])
 - Unavailable or insufficient nonclinical data should be considered as “effects detected” and the highest risk category assumed.
- IMP with demonstrated or suspected human teratogenicity/fetotoxicity
 - Highly effective contraception using methods with low user dependency

- Contraception during treatment and until the end of relevant systemic exposure. This period should be extended by 30 days in case of genotoxicity.
- Monthly pregnancy testing to be maintained until end of relevant systemic exposure – should be extended by 30 days in case of genotoxicity. Shorter testing intervals are to be considered depending on drug dosing schedule.
- IMP with possible human teratogenicity/fetotoxicity
 - Highly effective method of contraception
 - Contraception during treatment and until the end of relevant systemic exposure
 - Additional pregnancy testing to be considered; as a minimum, at the end of relevant systemic exposure
 - In each case of delayed menstrual period (over 1 month between menstruations) confirmation of absence of pregnancy is strongly recommended. This recommendation also applies to WOCBP with infrequent or irregular menstrual cycles.
- IMP with unlikely risk of human teratogenicity/fetotoxicity, for which assessment of the completed necessary nonclinical studies does not indicate teratogenicity/fetotoxicity, in early pregnancy and human data are not available or do not contradict these findings or there is already sufficient evidence for lack of risk based on human data
 - An acceptable effective method of contraception unless an absence of risk of human teratogenicity/fetotoxicity in early pregnancy can be justified
 - As a minimum, contraception until treatment discontinuation

Highly effective birth control methods:

Highly effective birth control methods are methods that can achieve a failure rate of less than 1% per year when used consistently and correctly are considered. Such methods include:

- Combined estrogen and progestogen hormonal contraception (oral, intravaginal, transdermal) associated with inhibition of ovulation; these should be initiated at least 7 days (for IMPs without suspected teratogenicity/genotoxicity) and 1 month (for IMPs potentially teratogenic/genotoxic) before the first dose of IMP
- Progestogen-only hormonal contraception (oral, injectable, implantable) associated with inhibition of ovulation; these should be initiated at least 7 days (for IMPs without suspected teratogenicity/genotoxicity) and 1 month (for IMPs potentially teratogenic/genotoxic) before the first dose of IMP
- Intrauterine device and intrauterine hormone-releasing system need to be in place at least 2 months before screening
- Bilateral tubal occlusion and vasectomized partner provided he is the sole sexual partner and has received medical assessment of the surgical process

- Sexual abstinence is **only** considered a highly effective method if defined as refraining from heterosexual intercourse in the defined period. The reliability of sexual abstinence needs to be evaluated in relation to the duration of the clinical study and the preferred and usual lifestyle of the patient.
- Periodic abstinence (eg, calendar, ovulation, symptothermal, post-ovulation methods), declaration of abstinence for the duration of a study, and withdrawal are **not** acceptable methods of contraception (according to Medicines and Healthcare Products Regulatory Agency).

Acceptable birth control methods:

Acceptable birth control methods that result in a failure rate of more than 1% per year include: progestogen-only oral hormonal contraception for which the inhibition of ovulation is not the primary mode of action; male or female condom with or without spermicide; cap, diaphragm, or sponge with spermicide. The combination of male condom with either cap, diaphragm, or sponge with spermicide (double barrier methods) are also considered acceptable but not highly effective methods of birth control.

Unacceptable birth control methods:

Periodic abstinence (calendar, symptothermal, post-ovulation methods), withdrawal (coitus interruptus), spermicides only, and lactational amenorrhea method are not acceptable methods of contraception. Female condom and male condom should not be used together.

Male contraception:

Male patients must always use a condom, except in cases of no genotoxicity or demonstrated or suspected human teratogenicity/fetotoxicity.

Vasectomy:

Use of contraceptive methods applies also to vasectomized men, because of the risk associated with transfer of a drug via seminal fluid.

Contraception for female partners of male study participants:

Female partners of male study participants must use contraception for non-pregnant WOCBP partner until the end of relevant systemic exposure in case of IMPs with genotoxicity or IMPs with no genotoxicity but demonstrated or suspected human teratogenicity/fetotoxicity.

Pregnancy tests in women of childbearing potential:

1. Conduct monthly pregnancy testing from first dose of IMP until last dose of IMP and additional 30 days in case the IMP does not have a marketing authorization and has suspected human teratogenicity/genotoxicity/fetotoxicity. Conduct monthly pregnancy testing and in case the IMP has a marketing authorization, if the IMP has a demonstrated or suspected human teratogenicity/genotoxicity/fetotoxicity according to SmPC. Shorter testing intervals are to be considered depending on drug dosing schedule.
1. Consider additional pregnancy testing, but at least at the end of relevant systemic exposure, in case of possible human teratogenicity/fetotoxicity. This refers to IMPs, for which human data on pregnancies is limited or not available, there is no suspicion of human teratogenicity based on class effects or genotoxic potential, and nonclinical

reproductive toxicity studies of relevance for early human pregnancy show positive findings that do not generate a strong suspicion of human teratogenicity/ fetotoxicity.

2. For IMPs with unlikely risk of human teratogenicity/fetotoxicity, additional pregnancy testing is generally not necessary. This refers to IMPs for which assessment of the completed necessary nonclinical studies does not indicate teratogenicity/ fetotoxicity in early pregnancy and human data are not available or do not contradict these findings or there is already sufficient evidence for lack of risk based on human data.

APPENDIX F. LOST TO FOLLOW-UP

A patient will be considered lost to follow-up if he/she repeatedly fails to return for scheduled visits and is unable to be contacted by the investigational center.

The following actions must be taken if a patient fails to return to the investigational center for a required study visit:

- The investigational center must attempt to contact the patient and reschedule the missed visit as soon as possible and counsel the patient on the importance of maintaining the assigned visit schedule and ascertain whether or not the patient wishes to and/or should continue in the study.
- In cases in which the patient is deemed lost to follow-up, the investigator or designee must make every effort to regain contact with the patient (where possible, 3 telephone calls and, if necessary, a certified letter to the patient's last known mailing address or local equivalent methods). These contact attempts should be documented in the patient's medical record.
- Should the patient continue to be unreachable, he/she will be considered to have withdrawn from the study with a primary reason of 'lost to follow-up'.

APPENDIX G. TOTAL BLOOD VOLUME

The total blood volume to be collected for each patient in this study is approximately 52 mL.

Total Blood Volumes

Type of samples	Volume per sample (mL)	Total number of samples	Total volume (mL)
Hematology (CBC with differential)	2 mL	5	10 mL
Serum chemistry tests with CPK	2 mL	6	12 mL
ADA	5 mL	5	25 mL
ADA Unscheduled	5 mL	1	5 mL
Total 1			52 mL

ADA= anti-drug antibody; CBC=complete blood count; CPK=creatine phosphokinase; mL=milliliters.

APPENDIX H. CLINICAL LABORATORY TESTS**Clinical Laboratory Tests**

Serum Chemistry	Hematology and Coagulation	Urinalysis
calcium phosphorus sodium potassium chloride creatine phosphokinase (CPK) bicarbonate or carbon dioxide glucose blood urea nitrogen (BUN) creatinine alanine aminotransferase (ALT) aspartate aminotransferase (AST) alkaline phosphatase (ALP) total protein albumin total bilirubin direct bilirubin indirect bilirubin follicle stimulating hormone (FSH), as required	hemoglobin hematocrit platelet count absolute neutrophil count WBC count and differential count -polymorphonuclear leukocytes (neutrophils) -lymphocytes -eosinophils (absolute values) -monocytes -basophils Human chorionic gonadotropin (HCG)	None

APPENDIX I. GLOBAL INITIATIVE FOR ASTHMA ICS CLINICAL COMPARABILITY TABLE

Post-Text Table 1: Rationale Medium or Higher Daily Doses of Inhaled Corticosteroids in Patients 12 Years and Older

Drug	Daily Dose (μg)	
	Medium	High
Beclomethasone dipropionate (CFC) ^a	>500	>1000
Beclomethasone dipropionate (HFA)	>200	>400
Budesonide (DPI)	>400	>800
Ciclesonide (HFA)	>160	>320
Fluticasone furoate (DPI)	N/A	≥200
Fluticasone propionate (DPI)	>250	>500
Fluticasone propionate (HFA)	>250	>500
Mometasone furoate	>220	>440
Triamcinolone acetonide	>1000	>2000

Source: Adapted from Box 8 in GINA 2016 Update (www.ginasthma.org).

^a Beclometasone dipropionate CFC is included for comparison with older literature.

CFC=chlorofluorocarbon propellant; DPI=dry powder inhaler; HFA=hydrofluoroalkane propellant; N/A=not applicable

APPENDIX J. ASTHMA CONTROL DIARY (ELECTRONIC DIARY)

(Sample provided in this appendix is for reference only.)

Handheld Spirometer

- You will need to perform your forced expiratory volume in 1 second (FEV₁) and peak expiratory flow (PEF) reading every morning using the handheld spirometer.
- You will need to perform your PEF every evening using the handheld spirometer.
- Blow into your handheld spirometer 3 times in the morning and 3 times in the evening.

Rescue Medication (Do not record SABA use for exercise pretreatment!)

Total number of puffs (daily):

[figure not shown]
Symptoms Post-injection:

[figure not shown]
- Have you received a study medication injection within the last 24 hours?
- Have you experienced any new symptoms since the study drug injection?

APPENDIX K. ASTHMA CONTROL QUESTIONNAIRE

(Sample provided in this appendix is for reference only.)

[figure not shown]

[figure not shown]

[figure not shown]

[figure not shown]
APPENDIX L. ASTHMA QUALITY OF LIFE QUESTIONNAIRE

[figure not shown]
(Sample provided in this appendix is for reference only.)

APPENDIX M. OPPORTUNISTIC INFECTIONS

Potential opportunistic infections include, but are not limited to, the following:

- *Acinetobacter* infection
- Aspergillosis
- Blastomycosis, extrapulmonary
- Burkitt's lymphoma
- Candidiasis of esophagus, bronchi, trachea, or lungs
- Cervical cancer invasive
- Coccidioidomycosis, disseminated or extrapulmonary
- Cryptococcosis, extrapulmonary
- Cryptosporidiosis infection, chronic intestinal (>1 month duration)
- Cytomegalovirus disease (other than liver, spleen, or nodes)
- Hepatitis B and C
- Herpes simplex bronchitis, pneumonitis, or esophagitis
- Herpes simplex ulcers chronic (>1 month)
- Herpes zoster (Shingles) when 2 distinct episodes or more than 1 dermatome
- Histoplasmosis disseminated or extrapulmonary
- Human polyomavirus infection
- Isosporiasis, chronic intestinal (>1 month's duration)
- Kaposi's sarcoma
- Listeriosis
- Lymphoid interstitial pneumonia
- Lymphoma immunoblastic
- Lymphoma primary of brain
- *Mycobacterium avium* complex or *M. kansasii*, disseminated or extrapulmonary
Mycobacterium infections, other species or unidentified species, disseminated or extrapulmonary (eg, *M. haemophilum*, *M. fortuitum*, or *M. marinum*)
- *Mycobacterium* tuberculosis, any site, latent or active
- Nocardiosis
- *Pneumocystis jiroveci* infection
- Pneumonia, recurrent

- Polyomavirus (JC virus or BK virus)-associated nephropathy (including progressive multifocal leukoencephalopathy)
- *Salmonella* sepsis
- *Salmonella* septicemia, recurrent
- Shingles
- Toxoplasmosis of brain
- Any active tuberculosis
- Wasting secondary to human immunodeficiency virus (HIV)

Source: Modified from the Panel on Opportunistic Infections in HIV-Infected Adults and Adolescents. Guidelines for the prevention and treatment of opportunistic infections in HIV-infected adults and adolescents: recommendations from the Centers from Disease Control and Prevention, the National Institutes of Health, and the HIV Medicine Association of the Infectious Disease Society of America. Available at http://aidsinfo.nih.gov/contentfiles/lvguidelines/adult_oi.pdf.

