1.2.2.3.2. Infections

The immune response to helminthic parasitic infections may involve eosinophils; therefore, the clinical course of existing or new helminthic parasitic infections may be complicated by a mechanism of action that lowers blood and tissue eosinophil counts. The iv reslizumab clinical protocols had an exclusion criterion for patients with active or suspected helminth infestation/infection. The asthma Phase 3 studies were conducted in geographic regions in which helminth infections are prevalent, including South and Central America, Africa, and Asia. There were no helminth infections reported, and no difference was documented between the treatment groups in regard to adverse events that may be associated with gastrointestinal helminth infections.

The overall rate of infection adverse events was lower for reslizumab-treated patients versus placebo-treated patients, with the types of infection events reported consistent with what would be expected in a primarily adult patient population with an underlying condition of asthma. No opportunistic infections were reported.

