#### **8.3.1.2. Anaphylaxis and Hypersensitivity**

Anaphylaxis and hypersensitivity events will be defined based on:

- MedDRA SMQ: Anaphylactic Reaction
- MedDRA SMQ: Hypersensitivity

Summaries will be presented separately for both the broad (broad+narrow) and narrow preferred terms by previous double-blind treatment group.

Adverse events suspected by the investigator to be anaphylaxis events will be summarized by preferred term and double-blind treatment group. Supplemental information related to the relative timing, clinical manifestation, and treatment of these suspected events will be collected in a dedicated CRF and reported in the patient listings.

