#### **8.3.1.3. Malignancies**

Malignancies will be defined based on:

- MedDRA SMQ: Malignant Tumors

Summaries will be presented by preferred term and previous double-blind treatment group.

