### 8.3.1.6. Opportunistic Infections

Opportunistic infections will be defined based on the following list of terms, derived from the preferred term (PT) or low level term (LLT) summarized in [Table 4](#). Food and Drug Administration (FDA) terms provided are from the Panel on Opportunistic Infections in HIV-Infected Adults and Adolescents.

Summaries will be presented by preferred term and previous double-blind treatment group.

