**Table 4: List of Terms for Opportunistic Infections**

Term	Code	Level	List from Panel on Opportunistic Infections in HIV-Infected Adults and Adolescents	If LLT- under which PT
Acinetobacter infection	10051894	PT	Acinetobacter infection	
Acinetobacter bacteraemia	10064965	PT	Acinetobacter infection	
Aspergillus infections	10003486	HLT	Aspergillosis	
Blastomycosis	10005098	PT	Blastomycosis, extrapulmonary	
Epididymitis blastomycetes	10015001	PT	Blastomycosis, extrapulmonary	
Osteomyelitis blastomycetes	10031255	PT	Blastomycosis, extrapulmonary	
Burkitt's lymphomas	10006596	HLT	Burkitt's lymphoma	
Oesophageal candidiasis	10030154	PT	Candidiasis of esophagus	
Cerebral toxoplasmosis	10057854	PT	Toxoplasmosis of brain	
Meningitis toxoplasmal	10048848	PT	Toxoplasmosis of brain	
Cervix carcinoma	10008342	PT	Cervical cancer invasive	
Cervix carcinoma stage II	10008346	PT	Cervical cancer invasive	
Cervix carcinoma stage III	10008347	PT	Cervical cancer invasive	

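### The SAP closes the protocol's open-ended opportunistic-infection list, with no route for other reported infections, and carries its five cancers into eight rows of the infection summary

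*Protocol*

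**What the plan says.** Protocol 7.1.6 names infections, including helminth and opportunistic infections, among the adverse events of special interest that sites send to the sponsor's safety department by the serious adverse event process. It points to Appendix M for potential opportunistic infections. Appendix M opens with "Potential opportunistic infections include, but are not limited to, the following" and cites guidelines on opportunistic infections in HIV-infected patients as its source. Its entries include "Cervical cancer invasive" and four other malignancies. Newly diagnosed malignancy is a separate item in 7.1.6.

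SAP 8.3.1.6 states: "Opportunistic infections will be defined based on the following list of terms". The list is Table 4, and the only output described is a summary by preferred term and previous double-blind group. Table 4 contains rows such as "Cervix carcinoma stage II". Malignancies have their own summary in SAP 8.3.1.3, defined by "MedDRA SMQ: Malignant Tumors".

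For anaphylaxis, SAP 8.3.1.2 adds a second route beside the MedDRA queries: "Adverse events suspected by the investigator to be anaphylaxis events will be summarized by preferred term and double-blind treatment group". Section 8.3.1.6 has nothing comparable. The SAP introduction says the SAP prevails where it differs from the protocol. Table 7, the list of changes from the protocol, contains only the additional data cut.

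**The concern.** Sites are told that the list is illustrative, so they may properly report an opportunistic infection that is not on it. The analysis then recognises only what is on it. The table meant to answer whether opportunistic infections occurred can therefore miss an event that a site reported as one.

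The same table can also include a patient who had no infection. The cancers come from a list written for HIV-infected patients, and this study excludes patients with HIV (exclusion l). Both documents otherwise treat malignancy and infection as separate safety topics.

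Safety is the primary objective, there is no data monitoring committee, and the SAP outputs go into an interim report supporting a regulatory submission. When counts are expected to be at or near zero, the classification of one patient decides what the summary says.

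**Working it through.** The plan states no figure to reproduce, so the check is a row count and a comparison of the two definitions.

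**1. Open list against closed list.** Appendix M is expressly not limiting. SAP 8.3.1.6, by contrast, restricts the category to the rows of Table 4. I counted 89 rows: 74 preferred terms, 9 high level terms and 6 low level terms (74 + 9 + 6 = 89). The nine high level terms take in whole groups of terms, so the list is wider than 89 single codes, but it is still closed. The SAP sentence mentions only preferred and low level terms, which does not match those nine rows. Neither 8.3.1.6 nor Table 4 has an other, investigator-identified or medical-review category.

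**2. Where an off-list infection goes.**
- Opportunistic-infection summary (SAP 8.3.1.6): absent.
- On-treatment tables by system organ class and preferred term, if onset is in the treatment period (SAP 8.3): present.
- Patient listings, which cover all adverse events (SAP 8.3): present.
- Sponsor safety reporting and review (Protocol 7.1.6 and 3.4): present.

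**3. Cancers in the list.**

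| Appendix M entry | Table 4 rows | Number |
|---|---|---|
| Burkitt's lymphoma | Burkitt's lymphomas (high level term) | 1 |
| Invasive cervical cancer | Cervix carcinoma; stages II, III and IV (preferred terms) | 4 |
| Kaposi's sarcoma | Kaposi's sarcomas (high level term) | 1 |
| Immunoblastic lymphoma | Immunoblastic lymphoma (preferred term) | 1 |
| Primary brain lymphoma | Central nervous system lymphoma (preferred term) | 1 |

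1 + 4 + 1 + 1 + 1 = 8 rows from 5 entries; 8/89 = 9.0% of the rows.

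**4. Effect of one patient.** With the planned enrolment of about 360 as the denominator, 1/360 = 0.28%, or about 0.3%. One listed cancer raises a count of patients in this category by that amount; one off-list infection lowers it by the same amount. This supposes a count of patients with any listed event. The SAP describes only output by preferred term, so such a total row is an assumption.

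**The case against.** The strongest reply is that little is lost and nothing is hidden. A reader might infer that an off-list infection would be reported as zero, or would disappear. The documents do not support that: step 2 shows that it leaves one supplementary summary and remains everywhere else. The upward error is also visible, because output by preferred term would print a cervix carcinoma under its own name. Both points stand and limit the consequence.

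A reader might also infer that the SAP introduced the cancers. It did not: all five conditions are in Appendix M, and on this the two documents agree. A fix confined to the SAP would create a new mismatch.

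Nor is double counting established. Whether the Malignant Tumors query contains these terms depends on MedDRA content that the documents do not give, and nothing in SAP 8.3.1 makes the categories mutually exclusive. The absence of an overlap rule is fact; the overlap is probable.

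It is tempting to set the result against the statement about the iv programme, "No opportunistic infections were reported". Protocol 1.2.2.3.2 does not say how opportunistic infection was defined there, and no inferential comparison is planned, so that zero is context and not a benchmark.

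The anaphylaxis parallel is imperfect. Protocol 7.1.6.1 describes dedicated case report forms only for anaphylaxis/hypersensitivity and for CPK/muscle events, and SAP 8.3.1.3 to 8.3.1.5 also rely on MedDRA terms alone. The documents describe no field marking an event as opportunistic, so it cannot be assumed that the fix needs no further work. Table 4 appears to cover Appendix M's own entries, and exclusions for HIV or other immunodeficiency and for recent malignancy, with 36 weeks of treatment, make events unlikely.

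What these replies leave untouched is that the stated rule can misclassify in both directions in the one output built for this question.

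**Conclusion.** The concern holds for the opportunistic-infection summary only. As written, that summary leaves out an opportunistic infection reported under Protocol 7.1.6 but absent from Table 4, and it includes any of eight neoplasm rows derived from five Appendix M entries. The size is about 0.3 percentage points per patient at 360 patients, which matters only because the expected count is very low. The frequency of all adverse events, the primary endpoint, is unaffected.

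The row count and the absence of a second route come straight from the documents. Two things are assumed: that the Malignant Tumors query contains the eight terms, which affects only whether a cancer appears twice, and that a patient total will be read from the summary. This is a worthwhile improvement to a safety table and does not threaten the study's main result.

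**What to change.** In SAP 8.3.1.6:

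1. Keep the Table 4 summary and add a separate line for adverse events identified as opportunistic infections from the special-interest reports that the sponsor's safety department already receives under Protocol 7.1.6, whether or not they are in Table 4. Because 7.1.6 places opportunistic infections within infections generally, state who makes the identification.
2. Take the eight neoplasm rows out of the infection summary, or show them as a separate subgroup excluded from the infection count. First confirm that SAP 8.3.1.3 captures them.
3. Align Appendix M with the revised list, correct the sentence on term levels to include high level terms, and record the change in SAP Table 7.

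The cost is SAP and appendix wording, a code-list edit and a small reconciliation of safety reports with the clinical database. No additional patient assessments are implied. The drawback is that the list will no longer match its source panel's list exactly. Keeping the fixed Table 4 summary beside the new line preserves a reproducible, prespecified count.
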